2.0 STUDY OBJECTIVES

2.1 Primary Objective

2.1.1 Evaluate the safety of HLA-haploididentical DLI combined with conventional induction and consolidation chemotherapy in terms of unacceptable toxicity as defined in section 7.0.

2.1.2 Evaluate the efficacy of HLA-haploidentical DLI combined with conventional induction and consolidation chemotherapy in terms of one-year DFS.

2.1.3 Validate the use of the CGA in elderly AML and MDS patients undergoing cellular therapy

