7.0 EVALUATION CRITERIA AND DEFINITIONS

1. Standardized response criteria will be used following **National Comprehensive Cancer Network (NCCN)** recommendations found on the NCCN website: www.nccn.org.
2. GVHD will be graded with standard criteria (see Appendix II). Other toxicity will be graded as per the NCI Common Terminology Criteria for Adverse Events (CTCAE) version 4.0 (see Appendix III). Grade 3-4 will be reported.
3. Unacceptable toxicity will be defined as either:
 - a. Grade III or IV aGVHD of the gut or liver or Grade IV aGVHD of the skin lasting > 7 days;

Chemo with Adoptive Haplo DLI

- b. Other grade IV CTCAE toxicity attributable to the DLI (e.g. infusion reaction, and distinct from grade IV toxicity attributable to chemotherapy) and lasting > 7 days
 - c. Treatment-related mortality (TRM), keeping in mind that anticipated mortality from standard induction chemotherapy in the elderly ranges from 11% for subjects 55-65 years-old with ECOG 0 to 50% for subjects older than 75 years with ECOG 2 [1].
4. Disease-free survival (DFS) is the time from CR to relapse or death.
5. Overall survival (OS) is the time from start of therapy to either death or the last day of follow-up for that patient.
6. Event Free Survival (EFS) is the time from start of therapy to progression of AML or relapse or death.
7. Neutrophil recovery time is defined as the first of 3 consecutive days in which the ANC is $>0.5 \times 10^9/L$
8. Platelet recovery is defined as the first of 3 consecutive days in which the platelet count is $>20 \times 10^9/L$
9. PD1/PDL1/PDL2 expression (marker of T cell exhaustion)
- 10.

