11.0 STUDY DESIGN AND ANALYSIS

11.1 Primary Objectives:

10.1.1 Safety: Evaluate the safety of HLA-haploidentical DLI combined with conventional induction and consolidation chemotherapy in terms of unacceptable toxicity as defined in section 7.0.

A maximum of 30 subjects will be consented for a maximum of 21 evaluable subjects accrued to this protocol over a period of 2 years. Safety will be evaluated by the number of subjects with unacceptable toxicity as defined by any of the following:

- i. Grade III or IV aGVHD of the gut or liver or Grade IV aGVHD of the skin lasting > 7 days;
- ii. Grade IV CTCAE toxicity attributable to DLI (e.g. infusion reaction, as opposed to Grade IV CTCAE toxicity from chemotherapy) and lasting >7 days
- iii. Treatment-related mortality (TRM), keeping in mind that anticipated mortality from standard induction chemotherapy in the elderly ranges from 11% for subjects 55-65 years-old with ECOG 0 to 50% for subjects older than 75 years with ECOG 2 [1].

Simon's optimal two stage design will be applied. These rules permit the study to be closed early if there is evidence that the true unacceptable toxicity rate is ≥ 0.40 . The stopping rules in the table below will also allow us to test the null hypothesis that the true toxicity rate is ≥ 0.40 against the alternative hypothesis that the true toxicity rate is ≤ 0.20 . The Type I and II error rates for this design are 0.15 and 0.2, respectively. Given that the true toxicity rate is 0.40 (0.20), the probability of stopping the trial at Stage 1 to accept the null hypothesis is 0.7 (0.16). The significance level of this design is 0.15 and the power is 0.80.

| Stage | Total Accrual | Close study/therapy if number of subjects with unacceptable toxicity is \geq |
|-------|---------------|--|
| 1 | 11 | 4 (45%) |
| 2 | 21 | 7 (33%) |

Rates of unacceptable toxicity will be calculated and monitored with the stopping rules in the table above. Toxicity in the other categories will be informally monitored and tabulated by Type and Grade, but they will not be used to determine tolerability of the procedure.

Chemo with Adoptive Haplo DLI

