For purposes of toxicity monitoring, each patient will be followed for unacceptable toxicity until a toxic event occurs or until 8 weeks after last cell infusion, whichever comes first. Accrual will not be suspended while collecting data for the interim analyses. However, as soon as a boundary within a stage in the table above is crossed, the study will be closed to further accrual. This design and the above boundaries will constitute our stopping rules for safety.

11.1.2 Efficacy: Evaluate the efficacy of HLA-haploidential DLI infusion combined with conventional induction and consolidation chemotherapy in terms of donor-recipient chimerism and microchimerism.

The assessment of efficacy will be conducted after collecting data for a maximum of 21 evaluable subjects. Our primary efficacy endpoint is the 1-year DFS rate following adoptive transfer. Using the chi-square test, we will test the null hypothesis is the CR rate will be ≤ 0.20 against the true hypothesis that 1-year DFS rate is >0.45 . With 21 patients, we can test this with approximately 84% power with one-sided alpha level of 0.05. Additional efficacy endpoints include the CR rate, overall response rate (CR + partial response), OS, and count recovery. CR and overall response rates will be calculated with one-sided 90% confidence interval. DFS and OS will be estimated using the method of Kaplan and Meier. All statistical analyses will be conducted in conjunction with our co-investigator, [name]., Assistant Professor of Biostatistics and Bioinformatics.

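### The primary efficacy test puts its null on the CR rate and its alternative on 1-year DFS, and no rule says how patients who never reach CR count among the 21

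*Combined protocol and SAP*

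**What the plan says.** Objective 2.1.2 sets efficacy "chemotherapy in terms of one-year DFS". Section 11.1.2 agrees in one sentence: "Our primary efficacy endpoint is the 1-year DFS rate following adoptive transfer". Three other sentences in 11.1.2 bear on the test.

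- Its opening line frames efficacy "in terms of donor-recipient chimerism and microchimerism".
- The hypothesis sentence reads "we will test the null hypothesis is the CR rate will be ≤ 0.20 against the true hypothesis that 1-year DFS rate is >0.45", to be tested by chi-square.
- The power statement is "With 21 patients, we can test this with approximately 84% power with one-sided alpha level of 0.05".

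The CR rate has its own place in the same section: "Additional efficacy endpoints include the CR rate". Section 7.0, item 4, gives the definition: "Disease-free survival (DFS) is the time from CR to relapse or death". The sample size comes from the safety part of 11.1: "A maximum of 30 subjects will be consented for a maximum of 21 evaluable subjects accrued to this protocol". Neither section says what makes a subject evaluable.

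**The concern.** A null on one endpoint and an alternative on another cannot be tested together. If the null is corrected to 1-year DFS, a second gap remains. DFS runs from CR, so a patient who never reaches CR has no DFS time, yet the power is computed on 21 patients. Such patients are to be expected: section 3.1 gives CR rates of about 30-65% with standard induction, and section 3.7 gives 80.0% in the cited randomised study's cell-infusion arm.

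EFS in section 7.0, item 6, starts at the beginning of therapy. It is not the primary endpoint, and it does not list failure to reach CR as an event, so it does not fill the gap.

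This is the only formal test for a primary efficacy objective. Without a written rule, the denominator could be settled after the results are known.

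**Working it through.** **Inputs.** From 11.1.2: p0 = 0.20, p1 = 0.45, n = 21, one-sided alpha 0.05 (z = 1.645). The documents set no CR rate for this trial. I assume 80% (section 3.7, with cells) and 65% (top of the chemotherapy-alone range in section 3.1).

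**1. The plan's figure.** One-sample normal approximation, with null variance for the cut-off and alternative variance for power:

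power = Φ{[√n(p1 − p0) − z√(p0(1 − p0))] / √(p1(1 − p1))}

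= Φ{[√21 × 0.25 − 1.645 × 0.400] / √0.2475}
= Φ{(1.146 − 0.658) / 0.497} = Φ(0.980) = 0.837.

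This matches the stated 84%. It requires 0.20 and 0.45 on one binary endpoint, with 21 in the denominator.

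**2. The same test, exactly.** With X ~ Binomial(21, p):

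- P(X ≥ 7 | 0.20) = 0.109, too large.
- P(X ≥ 8 | 0.20) = 0.043, so the rule is to reject at 8 or more.
- P(X ≥ 8 | 0.45) = 0.803.

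The uncorrected chi-square has the same cut-off: z = (8/21 − 0.20)/√(0.16/21) = 2.07 at 8 successes, and 1.53 at 7. The power actually delivered is therefore about 80%.

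**3. Does the denominator matter?** Take 17 CRs among 21 patients, with 7 disease-free at 1 year.

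- CR patients only: P(X ≥ 7 | n = 17, 0.20) = 0.038, reject.
- All 21, no CR = failure: P(X ≥ 7 | n = 21, 0.20) = 0.109, do not reject.

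The uncorrected chi-square splits the same way (z = 2.18 for 7/17, 1.53 for 7/21).

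**4. Power if only CR patients count.** Let the number of CRs be M ~ Binomial(21, CR rate), and average over M, with M = 0 as no rejection. The first power column uses the formula in step 1; the last two columns apply the uncorrected chi-square rule with binomial probabilities.

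| Assumed CR rate | Approximate power | Chi-square power | Chi-square average actual alpha |
|---|---|---|---|
| 80% | 0.767 | 0.764 | 0.060 |
| 65% | 0.699 | 0.705 | 0.065 |
| All 21 counted | 0.837 | 0.803 | 0.043 |

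**5. What 0.45 means if all 21 count.** An overall rate of 0.45 needs 1-year DFS among CR patients of 0.45/0.80 = 56% at CR 80%, or 0.45/0.65 = 69% at CR 65%.

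**The case against.** The case for leaving the plan nearly alone is fair in several respects.

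- The endpoint slip can be corrected from the text, since objective 2.1.2 and 11.1.2 both name 1-year DFS and CR is listed separately. This stands.
- The text also points to a denominator: efficacy is assessed on the same 21 evaluable subjects as safety, and power is stated for 21. A patient never in remission is naturally not disease-free at 1 year. This stands as an inference, but it is not a rule, and the section 7.0 definition pulls the other way.
- Section 1.0 makes safety the first priority, only the toxicity boundaries close accrual, and CR, EFS and OS are reported as well. This lowers the severity. It does not settle how the formal test is carried out.

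A reader might infer more than the documents support:

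- **That 84% is an arithmetic error.** It is not; it is the normal approximation, with exact power a little lower.
- **That the trial is really a CR-only test with very low power.** No sentence sets up such a design. Exact CR-only power is 65% at CR 80% and 56% at CR 65%, but part of that fall is conservatism of the exact test (average alpha 0.027). Still lower figures need chemotherapy-alone CR rates, against the premise in section 6.3.2 that cells raise CR.
- **That 7/17 against 7/21 shows one hypothesis giving two answers.** The two fractions are different estimands set against the same 0.20. The example shows why the estimand must be fixed, not which answer is right.
- **That evaluable means 21 patients in CR.** This fits poorly with using the same 21 for safety. The 30 in section 11.1 are consented, and the plan does not say how many are treated.
- **That relapse will go unobserved in patients who stop early.** Appendix I, footnote 7, asks only for survival follow-up, but section 6.4.1 schedules visits at least every 3 months for 2 years on completing therapy. Whether those visits cover early stoppers is unclear.

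**Conclusion.** The concern holds in a limited form and should be fixed. The hypotheses as printed do not form one test, and the rule for patients without CR is missing. The first can be repaired from the text. The second can be inferred, with all 21 the better-supported reading, but the plan's DFS definition contradicts that inference.

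If all 21 count, stated power moves only from 84% to about 80%. If only CR patients count, approximate power is about 77% at CR 80% and 70% at CR 65%, and the uncorrected chi-square averages an actual alpha of about 0.06 rather than 0.05. These CR-only figures assume 21 treated patients, CR rates taken from the background sections, and a true 1-year DFS of 0.45 among CR patients. No accrual or stopping decision rests on this test; what is at risk is the reported efficacy conclusion.

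**What to change.** 1. Write both hypotheses on one endpoint: H0, 1-year rate ≤ 0.20; H1, rate > 0.20; powered at 0.45. Change the opening line of 11.1.2 from chimerism to that endpoint.
2. Define evaluable. State that all 21 are in the denominator and that a patient who never reaches CR is a failure. Confirm that 0.20 and 0.45 are meant on this all-patient scale, given step 5 of the working. Align the wording of objective 2.1.2 and section 7.0, and report DFS from CR among CR patients as a supporting estimate.
3. Restate power as about 80%, rejecting at 8 or more of 21, with actual alpha 0.043.
4. Say what following adoptive transfer means. It may only name the treatment, as in the Figure 1 legend, or it may start the 1-year clock at a date other than CR. Reconcile footnote 7 of Appendix I with section 6.4.1 so that relapse status to 1 year is recorded for CR patients who stop early.

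The cost is wording, a slightly less favourable stated power and a little more follow-up data. No extra patients are needed.

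### The 1-year DFS test pairs a CR null with a DFS alternative and leaves its denominator open; its approximate 84% power is 80.3% exactly, if all 21 subjects count

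*Combined protocol and SAP*

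**What the plan says.** Section 11.1.2 (Efficacy) names the endpoint: "Our primary efficacy endpoint is the 1-year DFS rate following adoptive transfer". The hypotheses follow in one sentence. Its first half reads "Using the chi-square test, we will test the null hypothesis is the CR rate will be ≤ 0.20" and its second half reads "against the true hypothesis that 1-year DFS rate is >0.45". The operating characteristics come next: "With 21 patients, we can test this with approximately 84% power with one-sided alpha level of 0.05". On timing and sample size the section says "The assessment of efficacy will be conducted after collecting data for a maximum of 21 evaluable subjects", and the safety paragraph of section 11.1 says "A maximum of 30 subjects will be consented for a maximum of 21 evaluable subjects accrued to this protocol over a period of 2 years".

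Section 7.0 defines the endpoint: "Disease-free survival (DFS) is the time from CR to relapse or death".

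Section 11.1.2 gives no rejection count. It also does not say whether a subject who never reaches CR is a failure or is left out of the 1-year DFS rate.

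**The concern.** Three things in this paragraph do not fit together.

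- **Power.** With 21 subjects the outcome is a whole number, so only certain pairs of type I error and power are possible. A figure of 84% at one-sided 0.05 has to be checked against those pairs.
- **Hypotheses.** The null and the alternative concern different quantities, a CR rate and a 1-year DFS rate. Read literally, the stated power belongs to no single test.
- **Denominator.** DFS that starts at CR is undefined for a subject who never achieves CR. Whether the test has 21 subjects or fewer depends on a convention the plan does not state.

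At stake is whether the result of one of the trial's primary objectives can be read without a choice made after the data are seen.

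**Working it through.** **Inputs.** From section 11.1.2: n = 21, p0 = 0.20, p1 = 0.45, one-sided alpha 0.05 (z = 1.645), one-sample chi-square test.

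**Step 1: reproduce the plan's figure.** The normal approximation for the one-sample chi-square (score) test, without continuity correction, is

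power = Φ{[(p1 − p0) − z·√(p0(1−p0)/n)] / √(p1(1−p1)/n)}.

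- √(0.20 × 0.80 / 21) = 0.0873
- √(0.45 × 0.55 / 21) = 0.1086
- [0.25 − 1.645 × 0.0873] / 0.1086 = 0.980
- Φ(0.980) = 0.8365

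This rounds to the stated 84%.

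**Step 2: find the count at which the named test rejects.** The statistic is z = (x/21 − 0.20) / 0.0873.

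| Successes x | z | Rejects at 1.645? | P(X ≥ x), rate 0.20 | P(X ≥ x), rate 0.45 |
|---|---|---|---|---|
| 7 | 1.53 | no | 0.1085 | 0.9036 |
| 8 | 2.07 | yes | 0.0431 | 0.8029 |
| 9 | 2.62 | yes | 0.0144 | 0.6587 |

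The chi-square test rejects from 8 upward. The exact binomial test has the same boundary, because 8 is the smallest count with a tail probability of at most 0.05 under 0.20. So 80.3% is the power of the test the plan already names; no change of method is needed to reach it. The type II error is 1 − 0.8029 = 19.7%, against 16% implied by the plan. No cutoff gives 84%: the choices are 90.4% with type I error 0.109, 80.3% with 0.043, or 65.9% with 0.014.

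**Step 3: see what the denominator does.** Section 7.0 starts DFS at CR. If subjects without CR were left out, n would be the number reaching CR. The plan gives no expected CR rate for its own patients. As an assumption I take the CR rates of the two arms of the randomised study described in section 3.7, 42.8% and 80.0%. Then 0.428 × 21 ≈ 9 and 0.80 × 21 ≈ 17. The exact binomial test of 0.20 against 0.45 at one-sided 0.05 gives:

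| CR patients | Reject at | Type I error | Power at 0.45 |
|---|---|---|---|
| 9 | 5 | 0.020 | 0.379 |
| 11 | 6 | 0.012 | 0.367 |
| 13 | 6 | 0.030 | 0.573 |
| 17 | 7 | 0.038 | 0.710 |

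The range is roughly 37% to 71%. Power does not rise steadily with n because the cutoff moves in whole steps.

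These figures are for the exact test. At such sizes the chi-square test need not share its region. With 13 patients, for example, 5 successes give z = (5/13 − 0.20)/√(0.16/13) = 1.66, which rejects, although P(X ≥ 5) under 0.20 is 0.099.

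**The case against.** The best defence is that nothing was miscalculated. The plan names a test, a level, a sample size and two rates; the standard formula for those inputs gives 83.65%; and the text calls the figure approximate. A reader might infer from the exact value that 84% is an arithmetic error. The documents do not support that: the figure is an approximation that is optimistic at n = 21.

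The gap is also small. The alternative is written as a rate above 0.45, and exact power is already 85.0% at 0.47, so 3.7 points is comparable to a shift of two percentage points in an assumed rate. Exact power stays above 80%, the true type I error is below 0.05, and 21 is also the second-stage total of the safety design. A reader might therefore infer that the trial is too small or needs more patients. Nothing here shows that.

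The named test, null rate, level and n already fix the cutoff at 8, so printing it adds clarity and does not fill a logical gap. That too is fair, provided n really is 21.

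None of this answers the mismatch between the CR null and the DFS alternative, or the open denominator. A third inference, that the true power is 37% to 71%, would also go too far. Basing the power on 21 patients suggests that everyone was meant to count. The lower range shows what an unstated convention could do, under an assumed CR rate.

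**Conclusion.** The paragraph should be corrected, mainly because the two hypotheses concern different endpoints and the denominator of the DFS rate is not fixed. The power statement is a lesser matter: 84% is a valid large-sample approximation, but the named test has power 80.3% at 0.45 with true type I error 0.043, about 3.7 points lower than stated.

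The 80.3% rests on four conditions: DFS is the quantity in both hypotheses; all 21 evaluable subjects are in the denominator; subjects without CR count as failures; and accrual reaches 21. The plan calls 21 a maximum and gives a 0.16 chance that the safety rule stops the trial at Stage 1 when the toxicity rate is 0.20. If only CR patients counted, and 9 to 17 of 21 reached CR, exact-test power would be roughly 37% to 71%.

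**What to change.** In section 11.1.2:

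1. Use the 1-year DFS rate in both the null and the alternative.
2. State that all 21 evaluable subjects form the denominator and that a subject who does not reach CR counts as a failure. This settles what is being estimated, so it should be said openly and not left to be read from the decision rule.
3. State the time origin of the 1-year point. Section 7.0 starts DFS at CR, whereas section 11.1.2 refers to the rate after adoptive transfer; the two need to be reconciled.
4. Replace the power sentence with, for example: *The null hypothesis that the 1-year DFS rate is ≤0.20 is rejected if at least 8 of 21 subjects are alive and disease-free at 1 year (exact one-sided type I error 0.043, power 0.80 at 0.45).*

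The cost is wording only. No patients are added and, with all 21 counted, the rejection region of the named test does not change. The stated power becomes slightly less favourable. If the sponsor intends a DFS rate among CR patients only, the rule above does not apply, and the cutoff and power must be worked out again for the expected number of CRs.

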6.4.7 Geriatric evaluation

Comprehensive geriatric assessment: Patients will be required to complete the CGA before induction and 8 weeks after the final round of cellular therapy. We have demonstrated previously that inpatient geriatric assessment and management has positively affected quality of life in the elderly cancer inpatient at no greater length of hospitalization or extra cost than usual care[39]. The CGA has been validated in CALGB studies in elderly patients with solid tumors (breast, colon, prostate cancers)[40]. The mean time to complete the assessment is 23 minutes. Most patients can complete the self-administered portion of the assessment without assistance, and there is no association between age or educational level and the ability to complete the assessment without assistance. Patients may require assistance from the research team for three items: 1) Blessed Orientation- Memory-Concentration (BOMC) test; 2) Timed Up and Go; and 3) Karnofsky performance status (KPS). The remainder of the CGA is either self-administered or administered by a research assistant if the patient requires assistance. The following domains of CGA will be measured: a) Functional Status: Activities of Daily Living, Instrumental Activities of Daily Living, Karnofsky Performance Rating Scale, Timed Up & Go, Number of Falls in Last 6 Months b) Comorbidity: Physical Health Section c) Cognition: Blessed Orientation-Memory-Concentration Test d) Psychological: Hospital

Chemo with Adoptive Haplo DLI

Anxiety and Depression Scale e) Social Functioning: MOS Social Activity Limitations Measure f) Social Support: MOS Social Support Survey: Emotional and Tangible Subscales, Seeman and Berkman Social Ties, and g) Nutrition: Body Mass Index, % Unintentional Weight Loss in the Last 6 Months.

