11.1.3 Geriatric assessment: Medians and frequencies will be used to describe the baseline characteristics of participants and performance on the CGA. Overall survival and associated 95% CI will be estimated as in Aim 1 and correlated with CGA measures. Cox proportional hazards models will be fit for each CGA measure as a predictor of OS, in unadjusted models and models controlling for age, gender, and ECOG score. We also will estimate the hazard ratios in adjusted Cox regression models for continuous variables. To assess the incremental impact of cognitive and physical function variables on predicting survival, we will use Integrated Discrimination Improvement as described for survival analysis by Chambliss et al.[41] and implemented in the RiskPredictionParams SAS Macro (macro version 8, Chapel Hill, NC). The variables included in the model will be those associated with survival in our analysis and included in Kantarjian's predictive model for early mortality[42]. Internal cross-validation of the model will be assessed using 1000 bootstrap replicates implemented in the RiskPredictionParams SAS macro. Logistic regression analysis will be used to investigate relationships between baseline CGA and exploratory outcomes of 30-day mortality and CR. Competing risk modeling will be used to investigate a differential effect of impairment in CGA measures by cause of death[43].

For correlative studies, probe ID's on Affymetrix U133A gene chip have been identified for the candidate cytokines and include: IL-6 (211000,

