2055207, 204864, 204863, 205945, 212196), IL-1 (39402, 205067, 10118, 208200, 201404, 216245), IL-2 (207849, 204116), TNF- α (211841, 211282, 210405, 211495, 211153, 207643, 207849), and CRP (207849, 204116). The mean value for each cytokine from the Luminex assay will allow us to identify patients with high or low levels of each cytokine, and relate them to genetic typologies. Correlations between the serum cytokine levels and mRNA gene expression level for the cytokines will be evaluated by Spearman correlation. Specifically, the range of genes will be related to the panel of cytokines. Statistical significance will be assessed controlling for Type-I error using Hochberg tests, which are less conservative relative to the more common Bonferroni corrections[44, 45]. In order to reduce the dimensionality of the problem further, in follow-up tests, we will assess if factorization of the cytokines is feasible (using Principal Components Analysis (PCA)), and, if so, the resulting components will be related to the genetic typologies. We note that skew will likely be present in the cytokine panel which can impact the factorization above. We will assess skew, and, if necessary, transform the variables individually to bring about approximate normality. All analyses will be conducted at a two-sided α -level of 0.05 using SAS statistical software, version 9.2 (SAS Institute Inc., Cary, NC). We will use Spearman's correlation to assess the relationship between the biologic markers (serum cytokines and gene expression values) and clinical markers (each domain on the CGA and ECOG PS). While this work is exploratory and it could be argued that there is no need to adjust for multiple testing we will adjust p-values by the Hochberg method to control the Type-I error rate inherent in multiple testing[46]. All statistical analyses will be conducted in conjunction with our co-investigator, [name].

11.2 Secondary Objectives:

11.2.1 Evaluate incidence and severity of acute GVHD.

In addition to monitoring the rate of grade III-IV aGVHD of the gut or liver and grade IV aGVHD of the skin as in 10.1.1, we will also monitor overall rates of GVHD. Rates will be calculated with one sided 85% confidence interval.

11.2.2 Evaluate incidence and severity of other adverse events.

We will monitor other adverse events as defined in sections 7.0 and 9.0. Rates will be calculated with one sided 85% confidence interval.

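### Section 11.1.3 picks CGA predictors from the same 21 to 30 patients and then bootstraps the model, without stating that selection is repeated in each replicate or that the CGA–survival tests are adjusted for multiplicity

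*Combined protocol and SAP*

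**What the plan says.** Section 2.1.3 lists as a primary objective: "Validate the use of the CGA in elderly AML and MDS patients undergoing cellular therapy". Section 6.4.7 names the measures, in seven domains from functional status to nutrition.

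Section 11.1.3 sets out the analysis in this order:

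- **Screening.** "Cox proportional hazards models will be fit for each CGA measure as a predictor of OS", both unadjusted and controlling for age, gender and ECOG score.
- **Model.** The incremental value of cognitive and physical function variables is assessed by Integrated Discrimination Improvement (IDI). The rule for entry is "The variables included in the model will be those associated with survival in our analysis", joined by *and* to inclusion in a cited early-mortality model.
- **Validation.** "Internal cross-validation of the model will be assessed using 1000 bootstrap replicates", run in the same named SAS macro.

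On multiplicity, the biomarker text later in 11.1.3 says of the marker correlations: "we will adjust p-values by the Hochberg method to control the Type-I error rate inherent in multiple testing". The same text calls that work exploratory. It also contains the only significance level that could govern the CGA screening, two-sided 0.05 for all analyses.

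On sample size, section 11.1 says: "A maximum of 30 subjects will be consented for a maximum of 21 evaluable subjects accrued to this protocol over a period of 2 years". Section 11.1.3 gives no expected number of deaths, no power and no analysis set for the CGA.

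**The concern.** Screening, fitting and validation all use one small cohort. A bootstrap corrects for optimism only in the steps it repeats. If variables are chosen once on the full data and each replicate merely refits them, the correction covers the estimation of a few coefficients. It does not cover the search that found them. A measure that looks prognostic by chance in about 21 patients tends to look prognostic in resamples of those same patients.

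The multiplicity control also sits in an odd place: it protects correlations the plan calls exploratory, while none is stated for the Cox tests that serve a primary objective. At stake is whether a CGA result reported as internally validated means what a reader will take it to mean. No stopping rule or efficacy decision depends on it.

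**Working it through.** **The plan's own figure.** Section 11.1.2 states: "With 21 patients, we can test this with approximately 84% power with one-sided alpha level of 0.05". This is for 1-year DFS, 0.45 against 0.20. By normal approximation, power = Φ[(√21 × 0.25 − 1.645 × √(0.20 × 0.80)) / √(0.45 × 0.55)] = Φ[(1.146 − 0.658) / 0.497] = Φ(0.98) = 83.7%. The figure reproduces, but it says nothing about the CGA model.

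**Inputs.**

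- *Candidates:* section 6.4.7 names 14 measures if the two social support subscales are counted separately, and 13 if they are counted as one. Six concern physical function or cognition: ADL, IADL, Karnofsky, Timed Up & Go, falls and the Blessed test.
- *Patients:* 21, with 30 as the upper case (section 11.1).
- *Threshold:* two-sided 0.05. Its use as the selection rule is an assumption.
- *Deaths:* not stated. Assumed 50–90% of 21, about 10 to 19.

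**Step 1: chance of a false selection.** For k independent null measures, P(at least one) = 1 − 0.95^k:

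- k = 6: 26%
- k = 13: 49%
- k = 14: 51%

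**Step 2: what the bootstrap then reports.** Null data were simulated with 21 patients, exponential survival, pairwise correlation 0.2 and selection by score test at p < 0.05. Each setting had 500 datasets with 150 bootstraps each. The C-index stands in for IDI, and no published prognostic variables are in the model, so the true value is 0.50. The C columns are means over datasets in which something was selected.

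| Measures | Deaths | Any selected | Apparent C | Corrected, variables fixed | Corrected, selection repeated | Corrected C > 0.60: fixed / repeated |
|---|---|---|---|---|---|---|
| 6 | 50% | 33% | 0.719 | 0.706 | 0.638 | 99% / 75% |
| 6 | 70% | 33% | 0.685 | 0.675 | 0.613 | 96% / 56% |
| 6 | 90% | 31% | 0.672 | 0.661 | 0.605 | 94% / 52% |
| 14 | 50% | 52% | 0.737 | 0.714 | 0.616 | 98% / 53% |
| 14 | 70% | 54% | 0.704 | 0.685 | 0.592 | 98% / 40% |
| 14 | 90% | 54% | 0.685 | 0.668 | 0.580 | 93% / 35% |

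Take 14 measures and 70% deaths. The optimism is 0.704 − 0.500 = 0.204. The fixed-variable bootstrap removes 0.704 − 0.685 = 0.019, or 9% of it. Repeating selection removes 0.704 − 0.592 = 0.112, or 55%.

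**Step 3: over all null trials.** Multiply the chance of any selection by the chance that corrected C exceeds 0.60. At 70% deaths:

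- 14 measures: fixed 0.54 × 0.98 = 53%; repeated 0.54 × 0.40 = 22%.
- 6 measures: fixed 0.33 × 0.96 = 32%; repeated 0.33 × 0.56 = 18%.

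**Step 4: sensitivity.** Two further simulations used 21 patients, 13 measures and about 75% deaths:

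- Correlation 0.2: any selection in 47% of trials; C 0.70 apparent, 0.68 fixed, 0.59 repeated.
- Independent measures: any selection in 52%; C 0.70, 0.69 and 0.60.

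With 30 patients and six measures, something is selected in 27–28% of trials; corrected C is 0.63–0.67 fixed and 0.59–0.62 repeated. With 30 patients, 14 measures and 50% deaths, the figures are 52%, 0.68 and 0.59.

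**Step 5: what a real effect would need.** The hazard ratio per SD for 80% power at two-sided 0.05 is exp[(1.960 + 0.842) / √deaths]. It is 2.33 with 11 deaths and 1.90 with 19, before any multiplicity adjustment.

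**The case against.** The strongest reply is that the plan leaves these steps open and does not state them wrongly. Much of that stands.

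- **Selection rule.** A reader might infer that measures enter on univariate p < 0.05. The plan gives no threshold for association, and it fits both unadjusted and adjusted models without saying which decides.
- **Published-model clause.** The *and* may mean an intersection, which would confine the search to variables in the published model. That list is not in the documents, so the size of the search cannot be fixed. The stated aim of measuring incremental value fits a union better, which would add parameters against perhaps 10 to 19 deaths.
- **Number of candidates.** The IDI step concerns cognitive and physical function only, so the lower range of false selection may be the relevant one.
- **Bootstrap scope.** A reader might infer that the plan restricts resampling to the chosen model. It is silent. Fixed variables are the natural reading, because the variables are defined first and *the model* is then passed to a macro, but the macro's behaviour cannot be checked here.
- **Sample.** Twenty-one is the evaluable cap, not a defined CGA set. The CGA is done before induction, and the schedule of events follows patients who stop therapy early for survival, so the number could approach 30.
- **Measure.** IDI itself was not simulated. With prognostic published variables in the model, a true C of 0.50 would no longer apply.

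These points narrow the claim and widen the range. They do not supply the missing statement on re-selection or the missing multiplicity control.

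**Conclusion.** The point holds as a gap in specification on a primary objective. On the natural reading, the validation figures will be optimistic whenever the search matters. With no true CGA effect, about a quarter to a half of trials select at least one measure (26–33% for six, 47–54% for 13–14). In those trials the fixed-variable bootstrap leaves C at about 0.66–0.71 with 21 patients, and somewhat lower with 30. Repeating selection gives about 0.58–0.64, which removes much of the optimism but not all.

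A reader might infer that a model built from noise is bound to look validated, or that the analysis can neither support nor refute the CGA. The figures do not support that: under the null nothing is selected in roughly half of trials with 13–14 measures and in about two thirds or more with six.

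The sizes rest on selection at 0.05, 50–90% deaths, the C-index in place of IDI, and a model without published prognostic variables. An intersection reading of the published-model clause would reduce them.

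**What to change.** In section 11.1.3:

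1. List the candidate CGA measures, the selection threshold, and whether the unadjusted or the adjusted Cox model decides.
2. State whether the published-model clause is an intersection or a union, and list that model's variables.
3. Define the CGA analysis set and give the expected number of deaths.
4. Repeat the full selection step inside every bootstrap replicate, and report optimism-corrected IDI and C-index from that procedure.
5. Apply the Hochberg method already in the plan to the family of CGA–OS Cox tests.
6. Because optimism remains at this sample size even with re-selection, describe the prediction model under 2.1.3 as exploratory.

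The cost is some programming, probably outside the macro, and less favourable discrimination figures. Hochberg adjustment will also raise the effect needed for significance above the hazard ratios of about 1.9 to 2.3 per SD shown above. No patient procedure or data collection changes.
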